Assignment to study arms is implemented at the level of the vaccination event, with all vaccination events scheduled during a phase assigned to the corresponding arm. T_1 , the beginning of Phase 1, denotes the time of participants' enrollment into the control arm. At time T_2 , the beginning of Phase 2, all participants are rolled over to the arm with reminders; at time T_3 , the beginning of Phase 3, all participants are rolled over to the arm with reminders combined with incentives. While T_2 and T_3 denote fixed points in calendar time, variation in delivery dates across participants results in between- and within-individual variation in the assignment of vaccination events across the three arms. **Table 2** shows all possible combinations of vaccination event assignments to study arms at the level of the participant. With dates of birth exogenously determining children's vaccination schedules, shifts in T_2 and T_3 directly affect the number of vaccination events that may be observed in each study phase. Based on the distributions of expected delivery and vaccination due dates, T_2 and T_3 are chosen such that the expected number of vaccination events is approximately equal across the three arms. With T_2 and T_3 being random in relation to mothers' delivery dates, and thus children's vaccination schedules, the assignment of vaccination events across arms may be considered quasi-random. Loss to follow-up and other reasons for non-delivery of vaccination reminders result in exposure indistinguishable from the control condition.

The assignment to study arms based on scheduled vaccination dates, and the simultaneous transition of all participants between study arms, address concerns that the individual randomization into, and co-existence of, incentive and non-incentive arms are not considered viable within closely-knit communities. While cluster randomization was considered as an alternative approach, the heterogeneity of clusters suggests that this approach would confound the effects of settings with the effects of reminders and incentives.

Study setting

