The study is conducted in two adjacent districts, one urban district (Mtwara Municipality) and one rural district (Mtwara District Council), in Mtwara Region in Southeastern Tanzania. In 2017, Mtwara Municipality had an estimated population of 115,132; Mtwara District Council had an estimated population of 130,757.[35] Owing to logistical considerations, the study area in the rural district is limited to a 30 kilometer (km) radius around the urban district.

Study participants

Eligible study participants are women, ages 16 or older, who are in the third trimester of pregnancy and have access to a mobile phone. The target enrollment is 400 women.

Recruitment

Participants are recruited from at least 4 urban and at least 8 rural health facilities and the surrounding communities. Eligible health facilities regularly provide childhood vaccinations. A combination of purposive and snowball sampling strategies is used for recruitment as follows: Eligible women presenting for antenatal care at participating facilities are approached by trained study personnel and offered enrollment in the study. To minimize biases from facility-based enrollment, participating women and local community leaders (*balozis*) are asked to identify other pregnant women in their community, who, if eligible, are also offered enrollment in the study.

Enrollment and informed consent

All individuals contacted for participation in the study are informed of the study purpose and procedures, as well as risks and benefits, during the informed consent process by study staff. Women are approached in person and are provided study information orally and in writing using an informed consent script in Kiswahili. Only consenting women are included in the study. Some women may access mobile phones via relatives, friends, or other designees: these persons are considered authorized agents for the purpose of this study. Authorized agents are not considered research subjects and, thus, are not independently consented. By designating authorized agents, participating women are considered to be providing implied consent for these agents to receive information on their behalf.

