For each participant, outcomes are observed at three time points (corresponding to timely vaccinations at 6, 10 and 14 weeks, respectively). The probability of timely vaccinations and its association with reminders and incentives will be analyzed using a random effects logistic regression model. The outcome variable is 1 if the vaccination was received on-time, and 0 if early, delayed, or not received at all. The primary covariates of interest are indicator variables for the receipt of reminders only (“*reminder*”) and the receipt of reminders with an incentive offer (“*reminder+incentive*”). For arm 1 the value of both covariates is 0 for all three time points. For outcomes in arm 2, the value for *reminder* (and for arm 3 the value for *reminder+incentive*) is 1 if the mHealth system confirmed delivery of the reminder, and 0 for all other observations. Additional covariates (e.g. mother’s education, rural vs. urban residence, recruitment from health facilities vs. the community) will control for differences in participant characteristics between study arms and their association with vaccination timeliness. Interactions of *reminder* and *reminder+incentive* with these covariates describe systematic variation in the effects of reminders and incentives on vaccination timeliness. Models will control for the number of phone-based contacts prior to or within the timeliness window for any given vaccination, and standard errors will be adjusted to account for clustering at the level of the health facility catchment area.

Statistical power

Across 400 participants we expect up to 1,200 data points on vaccination timeliness. Assuming (a) that these data points are distributed equally across the 3 study arms (standard of care; reminders only; reminders and incentive); (b) a 10% attrition rate; (c) equal cluster sizes of 10 women per health facility catchment area, with an intra-cluster correlation of 0.02; (d) 3 observations per child, with a within-child correlation of 0.2; (e) a baseline rate of vaccination timeliness of 65% in the control condition; and (f) a 10 (15) percentage point difference associated with reminders (reminders and incentives), the power ($\alpha=.05$, 2-tailed) to detect such difference is 72% (98%).

Dissemination

Results will be shared with stakeholders at the regional and national levels, presented at national and international conferences, and published in high impact academic journals.

Data sharing

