mHealth-Assisted Conditional Cash Transfers to Improve Timeliness of Vaccinations (MINT)

ClinicalTrials.gov ID NCT03252288

Statistical analysis

For each participant, outcomes are observed at three time points (corresponding to timely vaccinations at 6, 10 and 14 weeks, respectively). The probability of timely vaccinations and its association with reminders and incentives will be analyzed in a bivariable analysis and using a random effects logistic regression model. The outcome variable is 1 if the vaccination was received on-time, and 0 if early, delayed, or not received at all. The primary covariates of interest are indicator variables for the receipt of reminders only (“*reminder*”) and the receipt of reminders with an incentive offer (“*reminder+incentive*”). For arm 1 the value of both covariates is 0 for all three time points. For outcomes in arm 2, the value for *reminder* (and for arm 3 the value for *reminder+incentive*) is 1 if the mHealth system confirmed delivery of the reminder, and 0 for all other observations. Additional covariates (e.g. mother’s education, rural vs. urban residence, recruitment from health facilities vs. the community) will control for differences in participant characteristics between study arms and their association with vaccination timeliness. Interactions of *reminder* and *reminder+incentive* with these covariates describe systematic variation in the effects of reminders and incentives on vaccination timeliness. Models will control for the number of phone-based contacts prior to or within the timeliness window for any given vaccination, and standard errors will be adjusted to account for clustering at the level of the health facility catchment area.

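### Catchment area is used only to adjust standard errors, so area differences can shift the reminder and incentive estimates if timing or message delivery varies by area; area fixed effects would prevent this.

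*Protocol*

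**What the plan says.** **Design (Protocol, Assignment to study arms and transitions between arms).** "Assignment to study arms is implemented at the level of the vaccination event", according to the phase in which the event is scheduled. Cluster randomisation was considered and rejected because "the heterogeneity of clusters suggests that this approach would confound the effects of settings with the effects of reminders and incentives". The alternative relies on "the simultaneous transition of all participants between study arms" at two calendar dates, T_2 and T_3. These are set so that the total number of events is about equal across arms. Because the dates are taken to be random relative to births, "the assignment of vaccination events across arms may be considered quasi-random".

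**Recruitment (Protocol, Recruitment).** "Participants are recruited from at least 4 urban and at least 8 rural health facilities and the surrounding communities", by purposive and snowball sampling.

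**Analysis (Protocol and SAP, Statistical analysis).** Timeliness is analysed "using a random effects logistic regression model"; the level of the random effect is not stated. The SAP adds a bivariable analysis. The exposure indicators equal 1 only where the system confirmed delivery, so undelivered events in arms 2 and 3 are coded like control events. The covariate list is introduced as examples: mother's education, then "rural vs. urban residence, recruitment from health facilities vs. the community". Catchment area appears once, in that "standard errors will be adjusted to account for clustering at the level of the health facility catchment area".

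**The concern.** Arm is a function of calendar date. An area whose women enrol or deliver later contributes more of its events to arms 2 and 3. T_2 and T_3 balance total events, not events within each area. A second route needs no difference in timing: if messages reach phones less often in some areas, those areas supply more of the events coded as unexposed.

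If such areas are also more or less timely than the rest, the difference between areas is read as an effect of the intervention. Adjusting standard errors for clustering changes the width of the interval, not its centre. A rural/urban term absorbs only the part of the area difference that lies along that one division, whereas at least 12 facilities are planned. Because the phases run in a fixed order, the timing route affects the arm 3 contrast about twice as strongly as the arm 2 contrast.

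**Working it through.** The plan gives no figure for this bias. Its power statement supplies some inputs; the rest are assumptions.

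**From the Protocol (Statistical power):** 400 women less 10% attrition = 360 children with 3 events each (1,080 events, 360 per arm); within-child correlation 0.2; intra-cluster correlation 0.02; control rate 65%; expected effects 10 and 15 points.

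**Assumed:** 12 equal areas of 30 children; births uniform over 12 weeks within each area; area starts evenly spread over 0, 4 or 8 weeks; T_2 and T_3 at the terciles of all event dates; area timeliness falling linearly with start order (full alignment, the worst case).

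**Step 1: size of area differences.** SD = sqrt(0.02 × 0.65 × 0.35) = 6.7 points. Twelve areas at positions -5.5 to +5.5 have SD sqrt((144 - 1)/12) = 3.45, so each step later in the start order costs 6.745/3.452 = 1.95 points.

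**Step 2: bivariable contrast, 4-week stagger.** Events per area, in start order:
- arm 1: 42, 42, 39, 36, 33, 30, 28, 26, 24, 22, 20, 18
- arm 2: 30, 28, 29, 30, 31, 32, 32, 31, 30, 29, 28, 30
- arm 3: 18, 20, 22, 24, 26, 28, 30, 33, 36, 39, 42, 42

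The mean positions are -332/360 = -0.922, 0 and +0.922. The shifts are therefore 0.922 × -1.95 = -1.8 points (reminder) and 1.844 × -1.95 = -3.6 points (reminder+incentive).

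**Step 3: model with a child random effect.** In the linear approximation, bias = (X'V⁻¹X)⁻¹X'V⁻¹u, where u is the area effect of each event and V has within-child correlation 0.2.

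| Stagger | Analysis | reminder | reminder+incentive |
|---|---|---|---|
| 0 weeks | any | 0 | 0 |
| 4 weeks | bivariable | -1.8 | -3.6 |
| 4 weeks | child random effect, no rural/urban term | -1.3 | -2.6 |
| 4 weeks | with the term, 4 urban areas spread over the order | -1.3 | -2.6 |
| 4 weeks | with the term, 4 urban areas start first | -0.4 | -0.9 |
| 8 weeks | bivariable | -3.3 | -6.7 |
| 8 weeks | child random effect, no rural/urban term | -2.5 | -5.0 |
| 8 weeks | with the term, urban spread | -2.5 | -5.0 |
| 8 weeks | with the term, urban first | -0.7 | -1.8 |
| 4 or 8 weeks | area fixed effects | 0 | 0 |

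Signs reverse if later areas are the more timely ones. An alignment of 0.5 halves every shift.

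**Step 4: delivery route, no stagger.** Assume delivery averages 80%, with an SD of 10 points across areas, higher where timeliness is higher. The delivery-coded contrasts shift by about +0.9 to +1.4 points with a child random effect, and by about +1.6 in a linear-probability simulation. Area fixed effects brought this to zero or near zero.

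**Step 5: cost of fixed effects.** With 12 areas the model standard errors change by less than 1% (for example 3.88 to 3.85 points for reminder+incentive at 8 weeks). With 40 areas, the number implied by 10 women per area, they rise by 0.4% to about 4%. A random area intercept in place of fixed effects leaves roughly 45% to 75% of the bias, because it shrinks the area effects.

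**The case against.** A reader might infer that the Protocol contradicts itself, rejecting cluster randomisation for a fault that its own design shares. The documents do not support that. Under cluster randomisation each area would sit in one arm; here every area changes arm on the same dates, so setting is not tied to arm by design. Bias needs a further link between an area's timing or delivery and its timeliness, and the documents report none.

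A reader might also infer that comparisons within areas go unused. If the random effect is at child level, they are partly used, because comparisons within a child are also within an area. The gap between -1.8 and -1.3 points at 4 weeks shows this.

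Three further objections stand:
- The staggered start is an assumption. The Protocol refers to a figure and a table for the study activities, and neither can be read in the available text, so it cannot be said that a common start is missing from the plan.
- If area effects are unrelated to start order, the mean shift is about 0 and the mean absolute shift is 0.3/0.6 points (4 weeks) or 0.6/1.1 points (8 weeks). Take a design effect of (1 + 9 × 0.02)(1 + 2 × 0.2) = 1.652, so 360/1.652 = 217.9 effective events per arm. The sampling standard errors are then sqrt((0.2275 + 0.1875)/217.9) = 4.4 points and sqrt((0.2275 + 0.16)/217.9) = 4.2 points. Clustered standard errors are meant to cover chance imbalance of this kind.
- The covariate list is open, so area adjustment is left uncommitted, not excluded.

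None of this removes the point. Switching on common dates rules out complete confounding but does not balance areas across phases or across confirmed delivery, and the plan commits to nothing that would correct an imbalance.

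**Conclusion.** The concern holds as a conditional one. As written, the analysis lets area differences into the point estimates whenever enrolment, births or confirmed delivery differ by area in a way related to timeliness. Otherwise the bias is zero.

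Under the worst-case assumptions above, the shift is about -1.3 to -2.5 points for reminders (13% to 25% of the expected 10 points) and -2.6 to -5.0 points for reminders plus incentives (17% to 33% of the expected 15). These figures apply with no rural/urban term, or with urban areas spread over the start order. If urban areas start first and the term is included, about one third remains.

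The figures come from a linear approximation with the same effect in every area. The planned model is logistic, so the exact zero under fixed effects should be read as approximate there. This is a worthwhile and inexpensive improvement to the analysis; it does not show that the planned estimates will be biased.

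**What to change.** In the Statistical analysis sections of both the Protocol and the SAP:

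1. Add catchment-area fixed effects to the mean model of the primary analysis, and state that the random effect is at child level.
2. Keep the cluster-adjusted standard errors.
3. Stratify the SAP's bivariable comparison by catchment area.
4. Do not rely on a random area intercept for this purpose, since it removes only part of the bias.

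A table of events by area and phase, and of confirmed delivery by area, would show whether the issue arose in practice.

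The cost is wording: area must already be recorded for the standard errors. At 12 areas the model gains 11 parameters with standard errors essentially unchanged. At 40 areas it gains 39, with standard errors up to about 4% larger. Area fixed effects deal only with differences between areas. They do not address calendar trends, which the Protocol's Discussion lists as a limitation, or differences within an area between women whose messages were and were not delivered.

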With support from the National Immunization and Vaccines Development (IVD) program of the Tanzanian National Ministry of Health, Community Development, Gender, Elderly and Children, we are evaluating the efficacy of mobile phone-based vaccination reminders and incentives in the form of conditional financial transfers (CFTs) for offsetting demand-side barriers to timely vaccination. Per the recently released WHO classification of digital health interventions, the two key interventions in this study correspond to 1.1 Targeted client communication (specifically, 1.1.3 Transmit targeted alerts and reminders to clients), and 1.7 Client financial transactions (specifically, 1.7.3 Transmit or manage incentives to clients for health services.) [34] Our hypothesis is that reminders and incentives will increase timeliness of vaccinations relative to the status quo. The design and protocol of the evaluation are described below.

Methods/Design

Study aim

The aim of the study is to assess the efficacy of (1) mobile phone-based reminders, and (2) mobile phone-based reminders combined with incentives in the form of CFTs, for improving vaccination timeliness among children at 6, 10 and 14 weeks after birth, compared to the standard of care.

Outcome measures

The recommended schedule for vaccinations by age 1 year is presented in **Table 1**. The primary study outcome is whether or not a child received an on-time vaccination; the outcome is measured for vaccinations scheduled at 6, 10 and 14 weeks after birth. Secondary outcomes include vaccination coverage, in aggregate and for each of the vaccinations due at 6, 10 and 14 weeks after birth. Timeliness is defined as vaccination within 28 days of the scheduled vaccination due date. Coverage is defined as the percentage of children vaccinated.

Study design

The study design represents a quasi-randomized controlled trial that includes three phases, each corresponding to one study arm: 1) standard of care (no reminders or incentives); 2) mobile phone-based reminders; and 3) mobile phone-based reminders combined with incentives in the form of CFTs. Arm 1 serves as the control arm; arms 2 and 3 are intervention arms. The trial is enfolded by base- and end-line assessments (**Figure 1**).

Assignment to study arms and transitions between arms

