Mobile phone reminder system: Participants in Arms 2 and 3 receive reminders for upcoming vaccination appointments 1 week and 1 day before the vaccination due date. No reminders are associated with the EDD or the vaccination due at birth. Reminders are issued in the form of text messages to the mobile phone numbers of study participants or their designees. Prior to study implementation, messages were tested for comprehension using a structured template, and revised based on feedback received. The timing of messages is based on findings from a cross-sectional survey of 134 Tanzanian mothers of children ages 12-23 months. In that survey, 54% of women who indicated any mobile phone use wanted to receive reminders one week before the due date, 40% one day before the due date, and 6% on the due date. Data on comprehension are collected in the end-line survey to inform future implementations.

Incentive disbursement system: For each timely vaccination for which a reminder with an incentive offer was sent to a mobile phone, a payment in the form of a mobile phone airtime recharge voucher code (worth either TSH 1000 or TSH 2000) is sent to a mobile phone number specified by the participant. The two-tiered incentive amount, which was chosen ad hoc by the study team as appropriate to 'nudge' participants toward timely vaccinations without significantly changing their economic incentives, [37] is conditional upon the timing of vaccination (see below).

Technical implementation: The scheduling and sending of SMS messages and incentives is implemented via a custom-built task scheduling, execution, and event tracking application called mParis ("mobile phone assisted reminder and incentive system"). mParis, which was developed for another NIH-funded study (R01MH106388), is built using Flowable, a flexible, open source, Java-based, workflow engine (<https://www.flowable.org>). [38] The system is based at the Kilimanjaro Clinical Research Institute, in Moshi, Tanzania.

Study activities

Key events and related study activities are summarized in **Figure 1** and **Table 3**.

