Women providing informed consent are enrolled in the study. At the time of enrollment, a baseline survey is conducted with all participants to assess socio-demographic characteristics, mobile phone ownership and use, reproductive history, EDD for the current pregnancy, and vaccination knowledge, history of vaccinations in a prior child, if applicable, and previously experienced or anticipated barriers to vaccinations. Mobile phone numbers are obtained for mothers and any authorized agents. Surveys are implemented electronically on tablet devices

and conducted by study staff at health facilities, participants' homes, or other mutually agreed-upon locations.

Toward the end of Phase 1, all women are contacted by phone to ascertain birth dates and outcomes, and information on past and scheduled vaccinations. The information is used to generate child-specific vaccination schedules. In Phases 2 and 3, reminder messages are sent to registered mobile phone numbers 1 week and 1 day prior to each scheduled vaccination, and, if no vaccination confirmation is received, 2 weeks after the vaccination due date. Uniquely numbered cards, given to participants at each completed or rescheduled vaccination, allow participants to report vaccination dates via the USSD system. When no vaccination report is received via the USSD system, SMS, or phone calls from participants, study staff contact the participant by phone to verify whether and when a vaccination was received, and ascertain the due date for the next vaccination, if applicable. Recorded vaccination dates are used to iteratively update vaccination schedules and to re-schedule reminders.

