During Phase 3, reminder messages offer an incentive for each timely vaccination. The full incentive amount (TSH 2000; approximately \$0.90) is paid when a vaccination is received within 2 weeks (14 days) of the due date; half the incentive is paid if the vaccination is completed more than 2 weeks but within 4 weeks (28 days) after the vaccination due date. Incentive amounts are paid if the mother, despite going to the health facility as reminded, is asked to return for a vaccination at a later date. Payments for timely vaccinations are made via an SMS message that includes a network-specific mobile phone airtime recharge voucher code and is sent to a phone number specified by the mother. An in-person end-line survey, conducted 12 months after enrollment, assesses barriers to vaccinations, receipt and acceptability of reminders (Arms 2 and 3) and incentives (Arm 3), and records vaccination dates from participants' government-issued vaccination cards, allowing for comparisons with the data recorded in the mHealth system.

Data management

Password protected tablet devices are used to collect survey data from participants. Data transfer agreements (DTAs), signed by all participating institutions, guide the secure sharing of data between Tanzania and foreign collaborators. To ensure confidentiality, identifying information are collected, transferred, and stored separately from survey data. On-site study monitoring, performed by the Principal Investigators or their designees, is used to verify

compliance with human subjects and other research regulations and guidelines, assess adherence to the study protocol, and confirm the quality and accuracy of information collected and entered into the study database. All collaborators have access to the final data.

Statistical analysis

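### Arms follow the due date but late reminders and incentive wording follow the calendar phase, so events due in the 14 days before T_2 or T_3 can receive the next arm's message

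*Protocol*

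**What the plan says.** Assignment is by due date. The Protocol (Assignment to study arms and transitions between arms) has "all vaccination events scheduled during a phase assigned to the corresponding arm". The switch is simultaneous: at T_2 "all participants are rolled over to the arm with reminders", and at T_3 everyone moves again, to reminders with incentives.

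Messaging is described by phase. Under Study activities, "In Phases 2 and 3, reminder messages are sent to registered mobile phone numbers 1 week and 1 day prior to each scheduled vaccination", with a further message "if no vaccination confirmation is received, 2 weeks after the vaccination due date". The same section says "During Phase 3, reminder messages offer an incentive for each timely vaccination".

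Payment follows the offer. The incentive disbursement paragraph pays "For each timely vaccination for which a reminder with an incentive offer was sent to a mobile phone", without limiting this to events due in Phase 3. Half the amount is paid for a vaccination "completed more than 2 weeks but within 4 weeks (28 days) after the vaccination due date".

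The outcome window is given under Outcome measures: "Timeliness is defined as vaccination within 28 days of the scheduled vaccination due date".

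In the model (Statistical analysis, Protocol and SAP), both indicators are 0 for every arm 1 event. An arm 2 event can score 1 only on the reminder indicator, if delivery was confirmed.

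**The concern.** The arm is fixed on the due date, but an event stays open for another 28 days and a message can go out halfway through. If that message depends on the phase then in force, an event due shortly before a switch is analysed in one arm and handled under the next. No transition rule or washout appears, and nothing holds back the late message, or its incentive wording, for an event carried over from the previous phase.

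At stake are the contrasts the trial was set up to estimate. Some control events would have had a reminder, and some reminder-only events an incentive offer that could still be earned. The analysis would treat neither as such.

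**Working it through.** **Timing.** Take an event due d days before T_2, with 0 < d ≤ 14. Its late message falls 14 − d days after T_2, so in Phase 2 or on its first day. The window then has 28 − 14 = 14 days to run. The event remains arm 1 and is coded 0/0. At T_3 the same arithmetic gives an arm 2 event an offer at day 14, with the half payment still open for days 15-28.

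**Can the trigger fire?** Yes. Child-specific schedules are built from calls made toward the end of Phase 1 (Study activities), so the system can hold pending control events before T_2.

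**Share of events in the zone.** The plan gives no phase lengths and no figure for boundary events, so there is nothing of its own to reproduce. I assume births spread evenly over B weeks, due dates at 6, 10 and 14 weeks, and T_2 and T_3 at the terciles of due dates (the Protocol aims for about equal numbers of events per arm).

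- With births starting at week 0, all three due-date series overlap from week 14 to week B + 6. There, 1/B of all events fall due per week.
- Phase 2 lies inside that stretch for the values below. Its length is (1/3)/(1/B) = B/3 weeks, and T_2 = 10 + B/3.
- Reminder-only share in the last 2 weeks: (2/B)/(1/3) = 6/B.
- Control share: also 6/B if T_2 − 2 ≥ 14. For B = 13, T_2 = 14.33, and 1.67 of the 2 weeks lie where only two series run. The share is 3 × (1.67 × 2/39 + 0.33/13) = 33%.

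| Assumption | Phase 2 length | Control share | Reminder-only share |
|---|---|---|---|
| B = 13 weeks | 4.3 weeks | 33% | 46% |
| B = 26 weeks | 8.7 weeks | 23% | 23% |
| B = 39 weeks | 13 weeks | 15% | 15% |
| Phases of 180 days, even due dates | 180 days | 14/180 = 8% | 8% |

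**Events.** The Statistical power section gives 1,200/3 × 0.9 = 360 per arm after attrition. For B = 13 to 39 the zone holds about 55-120 control and 55-166 reminder-only events (28 per arm for 180-day phases). Being in the zone is not exposure: only events unconfirmed at day 14 get the message. If 35-60% are unconfirmed (an assumption), 19-72 control and 19-100 reminder-only events are exposed, or 10-17 per arm for 180-day phases.

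**Direction.** Let s1 and s2 be the shares in the zone and g1 and g2 the average gain in points per zone event. With the planned differences of 10 and 15 points:

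- reminder+incentive versus control: 15 − s1·g1
- reminder+incentive versus reminder: 5 − s2·g2
- reminder versus control: 10 + s2·g2 − s1·g1

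Suppose every zone event gains the whole next-arm increment (g1 = 10, g2 = 5). This is generous, since only unconfirmed events can gain. Over B = 13 to 39 the first becomes 11.7 to 13.5 points and the second 2.7 to 4.2 (14.2 and 4.6 for 180-day phases).

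The third depends on the gains. At B = 13, g1 = 10 and g2 = 5 give 10 + 2.3 − 3.3 = 9.0. Equal gains of 9 points give 10 + 4.2 − 3.0 = 11.2.

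**The case against.** The strongest reply is that phase may simply mean arm. Study design equates each phase with one arm, and the mobile phone reminder paragraph describes recipients as those in Arms 2 and 3. If messages follow the event's arm, there is no crossover. This reading is open, and Figure 1 and Table 3, which summarise the activities, are not visible here. But the reminder paragraph lists only the two pre-due messages, and nothing in the available text applies the arm-based reading to the late one. So what stands is an ambiguity to settle, not a proven contradiction.

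Second, the models adjust for phone-based contacts before or within the timeliness window. That might absorb part of the effect, but the covariate is not defined as counting text messages, and it would not recode an event's exposure.

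Third, a reader might infer that both intervention effects are pulled toward zero. The documents do not support this: an incentive offer sent to arm 2 events raises the reminder rate, against the effect of reminders sent to control events.

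Fourth, a reader might infer that the phases are short and the affected share therefore large. T_2 and T_3 are not stated, and a 13-week spread of births would mean enrolling almost all women at once, since the third trimester alone spreads births by about that much.

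**Conclusion.** The point holds on the literal text and deserves a correction. Following the plan as written can give events due in the 14 days before a switch the next arm's message inside their outcome window, without the model registering it. Provided the messages have some benefit, reminder plus incentive versus control is diluted and the arm 3 versus arm 2 difference shrinks. The net effect on reminder versus control cannot be signed.

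The zone holds about 15-33% of control and 15-46% of reminder-only events under the even-birth, tercile assumptions, and about 8% with 180-day phases. The exposed share is smaller by the fraction already confirmed at day 14. The effect of a single late message on women not yet confirmed is unknown.

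A reader might go on to infer a marked loss of power for the reminder comparison. That would require counting only the contamination of the control arm and assuming both a conversion rate and phase lengths that the documents do not give.

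**What to change.** 1. Reconcile the Protocol's assignment section, the reminder and incentive paragraphs, and Study activities. State whether the late message and the incentive wording follow the event's arm or the calendar date. Each choice has a consequence. If wording follows the arm, offer and non-offer messages coexist for a time after T_3, which the simultaneous transition was meant to avoid. Applied to pre-due messages too, it would start them up to 7 days before each switch. If messages follow the date, the crossover has to be handled in the analysis.

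2. Pre-specify in the SAP a supporting analysis that excludes events due in the 14 days before T_2 or T_3, or recodes them by logged message delivery. The scheduling system already tracks delivery, so exposure can be checked per event.

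The cost is fewer events and lower power in that supporting analysis if events are excluded; the primary analysis loses none. Excluding every event whose 28-day window crosses a switch would go too far. The late message reaches only the 14-day zone, and with B = 13 the wider rule would leave about 360 × (1 − 12/13) = 28 of 360 reminder-only events.
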